**Withdrawal criteria**

1. PLT remains less than  $20 \times 10^9/L$  after two weeks' treatment of avatrombopag in a maximum dose of 60

	
mg/d (Solution: receive other treatment after withdrawal from the study);
 
 
2. The participant or his legal guardian requests a withdrawal ;
 
3. c poor compliance(medicine taken less than 80% of the prescribed amount or more than 120% of the prescribed amount);
 
4. With requirement of a medicine that is prohibited in the study;
 
5. With adverse events that discontinues the study;
 
6. With some unexplained serious complications;
 
7. Be pregnant during treatment;
 
8. Deemed unsuitable for further study by the investigator.
 
 
Trial Termination
 
 
1. Sponsor decides to stop the trial for safety reasons;
 
2. Independent ethics committee decides to stop the trial;
 
3. Principal investigator decides to stop the trial.
 

Investigational Product
	
 
• Name: avatrombopag;
 
• Dosage form: tablet;
 
• Specification: 20 mg/tablet.
 

Treatment Design
	
 
• The whole study is divided into two stages, including 4-weeks' core study and 4-weeks' extended study;
 
• During the core study, participants are randomly assigned into the avatrombopag group and the rhTPO treatment group(standard group) with 1:1 ratio. The initial dose of avatrombopag is 20 mg/d. If the patient's PLT count remains less than <math>20 \times 10^9/L</math> after one week, the maximum dose was increased to 40 mg/d.
 
 
Avatrombopag will be taken orally with food. The rhTPO

will be subcutaneously injected with dosage of 300 U/kg/d;

- After the end of the core study, participants in the avatrombopag group who does not meet the withdrawal indication can be enrolled in the extended study and continue the avatrombopag treatment with a maximum dose of 60 mg/d. Participants who does not respond to treatment in the rhTPO group (PLT < 20\*10^9/L ) can also be enrolled in the extended study to receive avatrombopag treatment, by titrating avatrombopag in the dose of 20-60 mg/d according to the participants' condition;

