- Patients who achieved PLT reconstruction during the core study and the extended study period are followed up to 4 weeks after investigational product withdrawal, and PLT count is measured for one time during the follow up;
- Adjustment Indication: When PLT ≥ 50\*10^9/L excluding the factor of blood transfusion, the dosage of avatrombopag and rhTPO will be eventually decreased and stopped according to clinicians.

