
process
	
 
1. Informed consent;
 
2. Subject's demographic information and basic information;
 
3. Medical history, current treatment, concomitant medication;
 
4. Vital signs, physical examination;
 
5. Transplantation mode and preprocessing scheme;
 
6. Blood test: blood routine, blood biochemical (including liver and renal functions), virus infection;
 
7. Pregnancy tests (women of childbearing age);
 
8. Eligibility criteria review.
 
 
Visit 1(Day 15 after Allo-HSCT, Initial treatment)
 
 
1. Blood test: blood routine, blood biochemical (including liver and renal functions);
 
2. Vital signs, physical examination;
 
3. Concomitant medication, including PLT transfusion;
 
4. Adverse events.
 
 
Visit 2-9 (one visit per 1~2 weeks. Visit 2, day 21±2; visit 3, day 28±2; visit 4, day 35±2; visit 5, day 42±2; visit 6, day 49±2; visit 7, day 56±2; visit 8, day 62±2; visit 9, day 70±2 after Allo-HSCT)
 
 
1. Blood test: blood routine, blood biochemical (including liver and renal functions);
 
2. Vital signs, physical examination;
 
3. Concomitant medication, including PLT transfusion;
 
4. Adverse events;
 
 
(Participants who achieved PLT reconstruction during the core and extended study period directly enter the follow up period;
 
Participants who do not respond to the standard

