-----------------------	--------------------------------------------------------------------------------------------------------------------------------------------------------------------------------------------------------------------------------------------------------------------------------------------------------------------------------------------------------------------------------------------------------------------------------------------------------------------------------------------------------------------------------------------------------------------------------------------------------------------------------------------------------------------------------------------------------------------------------------------------------------------------------------------------------------------------------------------------------------------------------------------------------------------------------------------------------------------------------------------------------------------------------------------------------------------------------------------------------------------------------------------------------------------------------------------------------------------------------------------------------------------------------------------------------------------------------------------------------------------------------------------------------------------------------------------------------------------------------------------------------------------------------------------------------------------------------------------------------------

	
treatment can enter the extended study after visit 3 to receive avatrombopag treatment)
 
Visit 10 (day 28±5 after achieved PLT reconstruction)
 
 
1. Vital signs, physical examination;
 
2. Blood test: blood routine, blood biochemical (including liver and renal functions).
 
 
Long-term follow up is recommended.
 
Adverse events are closely observed and concomitant medication is recorded in detail during the study.

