#### **Statistical analysis method**

- PLT and other mean variation trends were processed by repeated measurement data analysis of variance; Kaplan-Meier survival analysis was used to estimate the recovery of PLT count, cumulative predicted survival rate, cumulative recurrence rate of malignant hematologic disease, cumulative mortality associated with transplantation, and cumulative incidence of GVHD, and log-rank test was performed. Independent sample nonparametric test was used to analyze the accumulative demand of PLT suspension. The statistical process and graph were all run on SPSS 13.0 software. All tests were bilateral, and  $P \leq 0.05$  was considered to be significant. The PLT recovery time, granulocyte implantation time and PLT infusion number were compared by one-way analysis of variance. OS and DFS are estimated by Kaplan-Meier method. Risk factor analysis: variables: age, sex, HLA match, CD34+ cell number, incidence of GVHD within 100 days after transplantation, CMV infection rate. Multivariate Cox regression analysis was performed on the factors with significant differences ( $P < 0.05$ ) by one-way analysis of variance.

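### The last scheduled visit depends on platelet response and almost never reaches day 100, so the 100-day GVHD variable lacks a common observation window and the survival-type analyses have no stated horizon

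*Combined protocol and SAP*

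**What the plan says.** All places are in the combined protocol and SAP.

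- **Treatment Design:** treatment has two stages, "including 4-weeks' core study and 4-weeks' extended study". Patients with platelet reconstruction are "followed up to 4 weeks after investigational product withdrawal", with one platelet count in that period.
- **Study process:** treatment starts at "Visit 1(Day 15 after Allo-HSCT, Initial treatment"). The last visit of the treatment period is "visit 9, day 70±2 after Allo-HSCT". Responders leave this schedule on reconstruction and have one further visit, "Visit 10 (day 28±5 after achieved PLT reconstruction"), which lists vital signs, physical examination and blood tests. No visit after visit 9 is scheduled for non-responders. Beyond that the plan says only "Long-term follow up is recommended", without length, schedule or content.
- **Statistical analysis method:** "OS and DFS are estimated by Kaplan-Meier method". Survival, relapse, transplant-related mortality and GVHD are also to be analysed by Kaplan-Meier with a log-rank test. No time horizon is given for any of these. The risk-factor variables include "incidence of GVHD within 100 days after transplantation" and the CMV infection rate.
- **Outcome Measure:** OS, DFS, relapse and transplant mortality are neither primary nor secondary outcomes. Transplant-related complications are a safety measure.

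**The concern.** The end of scheduled contact is set by platelet response, which is the trial's primary outcome. This matters in two ways.

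First, a variable defined over 100 days needs every patient observed for 100 days. If fast recoverers are seen for a shorter time than slow recoverers, less GVHD will be recorded in them even where the true risk is the same. If platelet recovery is the outcome of the risk-factor analysis (the section does not name one), GVHD could appear linked to slow recovery through the schedule alone. Kaplan-Meier censoring cannot repair this, because the variable enters as a covariate.

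Second, Kaplan-Meier and log-rank assume that patients who leave observation have the same prognosis as those who stay. Here the reason for leaving is response. If response is prognostic for death, relapse or GVHD, the censoring is informative.

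**Working it through.** **Inputs.** Treatment starts on day 15. Each stage lasts 28 days. Visit 9 is day 70±2. Reconstruction needs 7 consecutive days. Visit 10 is 28±5 days after reconstruction. All come from the Treatment Design, Outcome Measure and Study process rows.

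**Plan's own figure.** End of treatment = 15 + 28 + 28 = day 71, inside the stated 70±2. The schedule is consistent on this point.

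**Last scheduled visit.** For responders: reconstruction day + 28, window ±5.

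| Patient | Reconstruction | Last visit | With window |
|---|---|---|---|
| Earliest responder, 7-day run starting on or just after day 15 | day 21–22 | day 49–50 | 44–55 |
| Responder at end of core stage | day 42–43 | day 70–71 | 65–76 |
| Responder at end of extended stage | day 70 | day 98 | 93–103 |
| Non-responder | none | day 70 | 68–72 |

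A 7-day run already under way at screening could be complete on day 15. That would put the last visit at 15 + 28 = day 43 (38–48), so day 50 is not a strict minimum. Day 70 is an upper figure for non-responders, because no later visit is stated for those withdrawn earlier.

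**Who reaches day 100?** A nominal visit on day 100 needs reconstruction on day 100 − 28 = 72, after visit 9's nominal date. With the full +5 days it needs reconstruction on day 100 − 33 = 67 or later. No core-stage responder and no non-responder gets there.

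**Other anchor.** Treatment Design counts four weeks from product withdrawal, not from reconstruction. Stopping between day 22 and day 71 gives a last contact between 22 + 28 = day 50 and 71 + 28 = day 99. Where treatment continues past reconstruction, this is later than visit 10. Under either anchor the end still varies by patient, and the nominal date stays short of day 100.

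**Who remains late?** Counting from reconstruction, only extended-stage responders have scheduled contact after about day 76. In the rhTPO arm the extended stage is described as avatrombopag treatment for non-responders, so late scheduled contact in that arm comes from patients who have changed treatment.

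**The case against.** The strongest reply is that only scheduled visits end at these times. Long-term follow-up is recommended, the study lasts 1.5 years, transplant complications are a safety measure, and adverse events are observed from consent to the end of the study. This stands in part. Some GVHD, relapse and deaths will be captured up to the last visit. But the 1.5 years is not stated to be per patient, and nothing specifies what is collected after the last visit.

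A reader might infer that OS, DFS, relapse and transplant mortality cannot be estimated at all. The documents do not support that. No horizon is stated, and Kaplan-Meier allows unequal follow-up, so short-term curves are possible, though probably with few events.

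A reader might also infer a between-arm bias of known size from the planning response rates of 60% and 35%. That does not follow. Those rates cover every core-stage responder, with last visits from about day 50 to day 71, not only the earliest.

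An illustration shows the limits. Assume a GVHD risk of 40% by day 100, a constant hazard from day 0, and no link with response. The share occurring by day t is 1 − 0.6^(t/100): 23% by day 52, 30.1% by day 70 and 36% by day 86. The contrast of 23% with 36% is between early and late recoverers, not between arms. Now spread core-stage last visits evenly over days 50–71 and later responders' over days 71–98. The average recorded shares are 26.6% and 35.0%. The arms differ by 0.60 − 0.35 = 0.25 in core response, so the crude arm difference is 0.25 × (30.1 − 26.6) = 0.9 percentage points if no one responds later, and 0.25 × (35.0 − 26.6) = 2.1 if all the rest do. In a simulation under the same assumptions, Kaplan-Meier at day 70 returned 30.0% to 30.2% in both arms, against a true 30.1%. The 40% and the constant hazard are assumptions, and the documents give no figure for how risk differs by response.

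**Conclusion.** The point holds for scheduled follow-up. Last contact depends on response and ranges from about day 50 (±5) to about day 98 (±5). Core-stage responders finish by about day 71 (76 with the window), and non-responders on day 70±2.

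For the 100-day GVHD variable the defect is definite. Scheduled visits do not cover its window for any core-stage responder or non-responder, and the shortfall is largest in the fastest recoverers. A spurious association with platelet recovery is possible if recovery is the outcome of that analysis.

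For OS, DFS, relapse, transplant mortality and cumulative GVHD the conclusion is weaker. The analyses lack a horizon, and their censoring is informative only if response is prognostic. That is plausible, but the documents do not quantify it, so neither the existence nor the size of a between-arm bias is established.

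The day counts rest on the anchor used for visit 10; the conclusion does not. Importance is minor to moderate, since these analyses are not listed outcomes and the core-stage platelet response is unaffected.

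**What to change.** Add one fixed day-100 status record for every randomised patient, whatever the response and whether or not the patient was withdrawn: alive or dead with date, relapse, GVHD onset date, and CMV. Take it from the transplant chart or by telephone. Censor all these analyses at day 100, the only horizon that the plan itself names.

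If this is not wanted, delete the 100-day GVHD variable and the OS, DFS, relapse and transplant-mortality analyses that have no supporting follow-up.

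In either case, reconcile the two starting points for responder follow-up: product withdrawal in Treatment Design and reconstruction in Study process.

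The cost is one chart or telephone check and one CRF page per patient. Deletion needs only a text edit.

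### The Cox risk-factor analysis screens by one-way ANOVA, names no outcome and has no timing rule for GVHD and CMV, so its p-values are invalid and those two hazard ratios are open to bias

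*Combined protocol and SAP*

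**What the plan says.** The Statistical analysis method section of the combined protocol and SAP lists the candidates: "Risk factor analysis: variables: age, sex, HLA match, CD34+ cell number, incidence of GVHD within 100 days after transplantation, CMV infection rate". It then says "Multivariate Cox regression analysis was performed on the factors with significant differences", with P<0.05 in a one-way ANOVA as the entry rule. The same section applies ANOVA to the recovery times themselves: "The PLT recovery time, granulocyte implantation time and PLT infusion number were compared by one-way analysis of variance". Yet it also plans Kaplan-Meier curves and a log-rank test for platelet recovery.

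The Cox outcome is not named. Platelet recovery appears earlier in the paragraph, and the sentence just before the risk-factor list is "OS and DFS are estimated by Kaplan-Meier method". Treatment arm is not among the candidates. Nothing says whether GVHD and CMV are fixed, time-dependent or landmark variables.

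The Study process section sets the clock. Visit 1 is "Day 15 after Allo-HSCT, Initial treatment" and the last treatment-period visit is "visit 9, day 70±2 after Allo-HSCT". Also, "Participants who achieved PLT reconstruction during the core and extended study period directly enter the follow up period", with one further visit 28±5 days after reconstruction.

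**The concern.** Three features of the stated rule are unsound or incomplete.

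- **The screen.** Any Cox outcome is a time that can be censored. ANOVA has no way to use a censored time, so patients without the event must be dropped or given an arbitrary value. P-values from a model whose terms were chosen by significance in the same data no longer have their nominal meaning.
- **The post-baseline factors.** "incidence of GVHD within 100 days after transplantation, CMV infection rate" describes events that can occur after treatment start and after the outcome they are meant to explain. A single 100-day incidence variable screened by ANOVA is most naturally read as a fixed yes/no. That coding classifies patients by what happens to them later.
- **The unnamed outcome and unlisted arm.** Without the outcome, neither the direction nor the size of the bias can be settled in advance. Without arm, the model yields no treatment-adjusted estimate.

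At stake is a secondary report that GVHD or CMV predicts recovery or survival when the analysis produced all or part of the association.

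**Working it through.** The plan gives no event count, hazard ratio (HR) or power for the Cox model, so there is no stated figure to reproduce.

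**Inputs from the documents.** 1:1 allocation and response of 35% and 60% (Sample size estimation). 78 participants (Subject Number) and 190 (Sample size estimation); both are carried because both are stated. Treatment start on day 15, last treatment-period visit on day 70, one visit 28±5 days after reconstruction (Study process). A 4-week core study (Treatment Design).

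**1. Censoring.** Expected response is (0.35 + 0.60)/2 = 0.475, so 52.5% have no recovery time in the core study.

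**2. Selection.** With six null candidates tested at 0.05, P(at least one passes) = 1 − 0.95^6 = 0.265, assuming independence. Expected core responders are 39 × 0.35 + 39 × 0.60 = 37.05 at N = 78, or 6.2 per candidate. At N = 190 they are 95 × 0.35 + 95 × 0.60 = 90.25, or 15.0 per candidate.

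**3. Timing.** The GVHD window runs 100 − 15 = 85 days past treatment start. The core study ends near day 15 + 28 = 43, so 100 − 43 = 57 days of the window fall after it. A patient who recovers on day 30 has a last scheduled visit near day 30 + 28 = 58; a non-recoverer's is day 70. How long GVHD is observed at scheduled visits therefore depends on the recovery time.

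**4. Size of bias under fixed coding.** Large-sample Cox simulations with 60,000 patients. Assumptions for recovery: exponential times calibrated to 35% and 60% by 28 days (arm HR = ln 0.40 / ln 0.65 = 2.13), 56 days of follow-up, and GVHD in 30% to 50% with onset uniform over days 15 to 100. Assumptions for survival: GVHD in 40%, and 10% to 30% dead by day 100. GVHD share, onset and death rates are not in the documents.

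| Outcome | True GVHD HR | GVHD recorded | HR, fixed coding |
|---|---|---|---|
| Recovery | 1.00 | complete to day 100 | 0.99–1.01 |
| Recovery | 1.00 | to 28 days after recovery, otherwise day 70 | 0.79–0.83 |
| Recovery | 1.00 | to 28 days after recovery, otherwise day 100 | 0.56–0.63 |
| Recovery | 0.50 | complete to day 100 | 0.84–0.85 |
| Survival | 1.00 | to death or day 100 | 0.37–0.39 |

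The recovery rows have arm in the model; leaving it out moves each value by less than 0.02. Time-dependent coding gives 1.00 when the truth is 1.00 and 0.49–0.51 when it is 0.50. Another simulation of the second row, with 50% recovery by 4 weeks, gave 0.91–0.93, so that row is sensitive to what is assumed.

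Hand check of the survival row: with roughly uniform death and onset times, a patient who dies has on average half the window. About 20% of deaths then carry GVHD, against 40% of survivors, and (0.20/0.80)/(0.40/0.60) = 0.375.

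**5. Leaving out arm.** A baseline factor with true HR 2.00 is estimated at 1.95 (28 days of follow-up) or 1.90 (56 days), an attenuation of about 3% to 5%.

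**The case against.** The strongest reply is that the plan is silent rather than wrong on GVHD and CMV. No coding is stated, and an analyst could use time-dependent terms. Fixed baseline coding and platelet recovery as the outcome are things a reader might infer; the text states neither.

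The reply continues that a spurious recovery association needs GVHD recording to stop early. With complete 100-day data and no true effect, the HR is about 1.0. The variable is defined to day 100, cumulative GVHD incidence is planned, and long-term follow-up is recommended. Treatment Design also runs follow-up to 4 weeks after stopping the product, which may be later than 28 days after recovery. All of this stands, so truncated recording is a risk and not a stated feature.

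Precision matters too. With 37 events and 40% GVHD, SE(log HR) = 1/√(37 × 0.4 × 0.6) = 0.34. A spurious HR of 0.91 would have a 95% interval of about 0.47 to 1.76 and would raise the false-positive chance only from 5% to about 6%. At 0.79, z = ln 0.79 / 0.34 ≈ −0.70, and the chance is about 11%. A firm prediction that the trial will report GVHD as delaying recovery is not supported.

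The mention of ANOVA may be loose wording for univariable screening. If so, the censoring objection falls but the selection objection remains. As written, the text says ANOVA.

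Finally, the analysis is exploratory. No stated objective or listed outcome depends on it, and treatment is already compared by log-rank. That limits the severity but does not make the stated rule sound.

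**Conclusion.** The point holds as a minor fault in a secondary analysis. Two parts rest on the text alone: a screen that cannot handle censoring and invalidates the final p-values, and post-baseline candidates with no timing rule and no named outcome. The 26% figure assumes six independent null factors.

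The bias in the GVHD and CMV hazard ratios is conditional on fixed yes/no coding. It is large if the outcome is survival (0.37–0.39 for a null effect). For recovery it is a dilution (0.50 becomes 0.84–0.85), or a spurious association if recording stops at the last scheduled visit. Every one of these sizes uses assumed GVHD and death rates. CMV was not simulated; the same reasoning applies, but no size is claimed.

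A reader might infer that all the model's hazard ratios are biased, or that leaving out arm confounds them. Neither follows. Age, sex, HLA match and CD34+ cell number are baseline factors, and omitting a randomised arm attenuates such effects only by about 3% to 5% here. The primary endpoint is a proportion in the core study and is untouched.

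**What to change.** Replace the risk-factor sentences in Statistical analysis method with the following:

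- Name the Cox outcome and its time origin. If there is more than one outcome, give one model for each.
- Drop the ANOVA screen. Pre-specify treatment arm plus age, sex, HLA match and CD34+ cell number. If each takes one parameter, five terms on 37 expected core responders is 37.05/5 = 7.4 events per term (90.25/5 = 18.1 at N = 190).
- Enter GVHD and CMV only as time-dependent covariates or by landmark, or leave them out.
- For time to platelet reconstruction, restrict the arm comparison to the core study, or censor when rhTPO non-responders switch to avatrombopag. The switch follows from non-response, so censoring at it is not independent of the outcome; a common cut-off avoids this. Treatment Design places the switch after the core study (about day 43), while Study process allows it after Visit 3 (day 28±2). These passages must be reconciled before the cut-off is written.

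Cost: a few lines of SAP wording, and onset dates for GVHD and CMV if they are kept. Check too that the case report form captures HLA match and CD34+ cell number, which the screening list in Study process does not name. The sample size does not change.
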